#### **4.1.2 Exclusion Criteria**

Patients who meet any of the following criteria will be excluded from study entry:

- *Grade 3b follicular lymphoma*
- *History of transformation of indolent disease to DLBCL*
- Known CD20-negative status at relapse or progression
- Central nervous system lymphoma or leptomeningeal infiltration
- Prior allogeneic SCT
- Completion of autologous SCT within 100 days prior to Day 1 of Cycle 1

- History of resistance to lenalidomide or response duration of < 1 year (for patients who had a response to a prior lenalidomide-containing regimen)
- Prior standard or investigational anti-cancer therapy as specified below:
  - Lenalidomide, fludarabine, or alemtuzumab within 12 months prior to Day 1 of Cycle 1
  - Radioimmunoconjugate within 12 weeks prior to Day 1 of Cycle 1
  - Monoclonal antibody or ADC therapy within 5 *half-lives* or 4 weeks prior to Day 1 of Cycle 1, *whichever is longer*
  - Radiotherapy, chemotherapy, hormonal therapy, or targeted small-molecule therapy within 2 weeks prior to Day 1 of Cycle 1
- Clinically significant toxicity (other than alopecia) from prior therapy that has not resolved to Grade  $\leq 2$  (per NCI CTCAE, Version 4.0) prior to Day 1 of Cycle 1
- Treatment with systemic immunosuppressive medications, including, but not limited to, prednisone, azathioprine, methotrexate, thalidomide, and anti-tumor necrosis factor agents within 2 weeks prior to Day 1 of Cycle 1
  - Treatment with inhaled corticosteroids and mineralocorticoids is permitted.
  - If corticosteroid treatment is urgently required for lymphoma symptom control prior to the start of study treatment, up to 100 mg/day of prednisone or equivalent can be given for a maximum of 5 days, but all tumor assessments must be completed prior to initiation of corticosteroid treatment.
- History of severe allergic or anaphylactic reaction to humanized or murine monoclonal antibodies
- Known sensitivity or allergy to murine products or any component of obinutuzumab, *rituximab*, polatuzumab vedotin, or lenalidomide formulations
- History of erythema multiforme, Grade  $\geq 3$  rash, or desquamation (blistering) following prior treatment with immunomodulatory derivatives such as thalidomide and lenalidomide
- Active bacterial, viral, fungal, or other infection
  - Caution should be exercised when considering the use of obinutuzumab *and rituximab* in patients with a history of recurring or chronic infections.
- Positive for hepatitis B surface antigen (HBsAg), total hepatitis B core antibody (HBcAb), or hepatitis C virus (HCV) antibody at screening
- Known history of HIV positive status
  - For patients with unknown HIV status, HIV testing will be performed at screening if required by local regulations.
- History of progressive multifocal leukoencephalopathy
- Vaccination with a live virus vaccine within 28 days prior to Day 1 of Cycle 1
- History of other malignancy that could affect compliance with the protocol or interpretation of results, with the exception of the following:

Curatively treated carcinoma in situ of the cervix; good-prognosis ductal carcinoma in situ of the breast; basal- or squamous-cell skin cancer; Stage I melanoma; or low-grade, early-stage localized prostate cancer

Any previously treated malignancy that has been in remission without treatment for  $\geq 2$  years prior to enrollment

- Contraindication to treatment for TE prophylaxis (see Section 4.3.2.5)
- Grade  $\geq 2$  neuropathy
- Evidence of any significant, uncontrolled concomitant disease that could affect compliance with the protocol or interpretation of results, including significant cardiovascular disease (such as New York Heart Association Class III or IV cardiac disease, myocardial infarction within the previous 6 months, unstable arrhythmia, or unstable angina) or significant pulmonary disease (such as obstructive pulmonary disease or history of bronchospasm)
- Major surgical procedure other than for diagnosis within 28 days prior to Day 1 of Cycle 1 or anticipation of a major surgical procedure during the course of the study
- Inadequate hematologic function (unless due to underlying lymphoma), defined as follows:
  - Hemoglobin  $< 9$  g/dL
  - ANC  $< 1.5 \times 10^9/L$
  - Platelet count  $< 75 \times 10^9/L$
- Any of the following abnormal laboratory values (unless due to underlying lymphoma):
  - Calculated creatinine clearance  $< 50$  mL/min (using the Cockcroft-Gault formula; see Appendix 7)
  - AST or ALT  $> 2.5 \times ULN$
  - Serum total bilirubin  $> 1.5 \times ULN$  (or  $> 3 \times ULN$  for patients with Gilbert syndrome)
  - INR or PT  $> 1.5 \times ULN$  in the absence of therapeutic anticoagulation
  - PTT or aPTT  $> 1.5 \times ULN$  in the absence of a lupus anticoagulant
- Pregnant or lactating, or intending to become pregnant during the study
  - Women of childbearing potential must have two negative serum pregnancy test results (minimum sensitivity, 25 mIU/mL) prior to initiating therapy: at 10–14 days prior to Day 1 of Cycle 1 and within 24 hours prior to Day 1 of Cycle 1.
- Life expectancy  $< 3$  months
- Unable to comply with the study protocol, in the investigator's judgment

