## 4.2 METHOD OF TREATMENT ASSIGNMENT

This is a Phase Ib/II, open-label, multicenter, non-randomized, dose-escalation study of G+Pola+Len in patients with R/R FL and R+Pola+Len in patients with R/R DLBCL.

During the dose-escalation phase, patients will be assigned to cohorts with varying polatuzumab vedotin (*R/R FL dose-finding only*) and lenalidomide dose combinations, through use of an interactive voice or web-based response system (IxRS). During the *FL* expansion phase, patients *with R/R FL* will receive obinutuzumab in combination with lenalidomide at the *FL* RP2D and polatuzumab vedotin at the RP2D as induction treatment. *During the DLBCL expansion phase, patients with R/R DLBCL will receive rituximab and polatuzumab in combination with lenalidomide at the DLBCL RP2D.* Post-induction treatment (for eligible patients only) will depend on lymphoma histology. Patients with *FL* will receive maintenance treatment with obinutuzumab and lenalidomide, and patients with *DLBCL* will receive consolidation treatment with *rituximab* and lenalidomide (see Section 3.1.1 for details).

Enrollment tracking will be performed through use of the IxRS. Prior to initiating screening, the study site should confirm via the IxRS that slots are available for enrollment. After written informed consent has been obtained and preliminary eligibility has been established, the study site will submit documentation supporting eligibility to the Sponsor and obtain the Sponsor's approval to enroll the patient. Once the Sponsor reviews and approves the patient for enrollment, the patient number will be assigned and the patient will be enrolled via the IxRS. The Sponsor will communicate to the sites impending closure of screening.

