### **5. ASSESSMENT OF SAFETY**

#### **5.1 SAFETY PLAN**

Polatuzumab vedotin is not a marketed product, and *lenalidomide* is not approved for the treatment of patients with R/R FL. *Obinutuzumab* is only approved in combination with bendamustine for the treatment of R/R FL. *Rituximab* and *lenalidomide* are not approved for the treatment of patients with R/R DLBCL. Clinical development is ongoing. The safety plan for patients in this study is based on clinical experience with *obinutuzumab*, *rituximab*, *polatuzumab vedotin*, and *lenalidomide* in completed and ongoing studies. The anticipated important safety risks of *obinutuzumab*, *rituximab*, *polatuzumab vedotin*, and *lenalidomide* are outlined below. Please refer to the *Obinutuzumab*, *Rituximab*, and *Polatuzumab Vedotin Investigator's Brochures* and the

lenalidomide Summary of Product Characteristics (SmPC) for a complete summary of safety information.

Several measures will be taken to ensure the safety of patients participating in this trial. Eligibility criteria have been designed to exclude patients at higher risk for toxicities (see Section 4.1). Patients will undergo adequate safety monitoring during the study, including assessment of the nature, frequency, and severity of adverse events, as described in this section and in Section 4.5. In addition, guidelines for managing adverse events, including criteria for dosage modification and treatment delays or discontinuation, have been provided (see Section 5.1.7).

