#### **Neutropenia**

Neutropenia and neutropenia-associated events resulted in protocol-mandated dose reductions and/or delays. Serious neutropenia including febrile neutropenia has been reported during treatment with polatuzumab vedotin. Patients with inadequate hematologic function will be excluded from this study (see Section 4.1.2). Patients receiving study treatment will be regularly monitored for evidence of marrow toxicity with complete blood counts. Treatment may be delayed for hematologic toxicities as described in Section 5.1.7.3. The use of G-CSF for neutropenia is described in Section 4.4.1.

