#### **5.1.4.8 Renal Impairment**

Lenalidomide is substantially excreted by the kidney. Patients with renal impairment (i.e., calculated creatinine clearance  $< 50$  mL/min) will not be enrolled in this study. Renal function will be monitored during the study, and the lenalidomide dose may be adjusted as outlined in Section [5.1.7.2](#) (see [Table 19](#)).

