### 5.1.7 Management of Specific Adverse Events

Study treatment may be delayed for toxicity for a maximum amount of time, as specified in [Table 17](#), [Table 18](#), and [Table 19](#). If study treatment is delayed for longer than the specified maximum amount of time, study treatment will be permanently discontinued. When a treatment cycle is delayed because of toxicity resulting from any component of the regimen, all study treatment should be held and resumed together to remain synchronized. If one drug is discontinued, treatment with the other two drugs may be continued for patients experiencing clinical benefit as determined by the investigator after discussing with the Medical Monitor.

Treatment delays apply to all toxicities described below; dose modifications apply only to toxicities that are considered to be related to lenalidomide or polatuzumab vedotin (only for peripheral neuropathy). There will be no dose reductions of obinutuzumab or *rituximab*. *For patients receiving obinutuzumab, if toxicity occurs before Cycle 1 Day 8 or Cycle 1 Day 15, these doses of obinutuzumab will not be skipped but given after resolution of toxicity.*

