**Table 19 Guidelines for Management of Non-Hematologic Toxicities During Induction**

Event		Action to Be Taken
General guidance for treatment delays and discontinuation		
 
– If study treatment is withheld for >21 days because of a toxicity that is attributable to study treatment, permanently discontinue study treatment.
 
– When a treatment cycle is delayed because of toxicity resulting from any component of the regimen, all study treatment should be held and resumed together to remain synchronized.
 
– If one drug is discontinued, treatment with the other two drugs may be continued for patients experiencing clinical benefit as determined by the investigator after discussion with the Medical Monitor.
 

IRRs and anaphylaxis		
 
– Guidelines for the management of IRRs are provided in Section 4.3.2.1 for obinutuzumab, Section 4.3.2.2 for rituximab, and Section 4.3.2.3 for polatuzumab vedotin.
 
– In case of anaphylaxis, study treatment should be permanently discontinued.
 

Renal toxicity		
 
– Adjust the dose of lenalidomidea as outlined below: 
 
• If creatinine clearance is <math>\geq 30</math> but <math>< 50</math> mL/min, lenalidomide should be given at a dose of 10 mg/day.
 
• If creatinine clearance is <math>< 30</math> mL/min and dialysis is not required, lenalidomide should be given at a dose of 10 mg every other day.
 
• If creatinine clearance is <math>< 30</math> mL/min and dialysis is required, lenalidomide should be given at a dose of 5 mg/day. On dialysis days, the dose should be administered after dialysis.
 
 
 

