**Table 19 Guidelines for Management of Non-Hematologic Toxicities During Induction (cont.)**

Event		Action to Be Taken
Other non-hematologic toxicities (i.e., not described above), excluding alopecia, nausea, and vomiting	Grade 3 or 4	
Grade 4 events
 
 
– Permanently discontinue study treatment.
 
 
Grade 3 events
 
 
– Withhold study treatment.
 
– If improvement to Grade <math>\leq 1</math> or baseline, resume obinutuzumab or rituximab at full dose and, if the event is considered related to lenalidomide, resume lenalidomide accordingly at a reduced dose as per guidelines in Section 5.1.7.2 for current and subsequent cycles.
 
– No more than two dose reductions of lenalidomide are allowed.
 

	Grade 2	
 
– Withhold study treatment.
 
– If improvement to Grade <math>\leq 1</math> or baseline, resume obinutuzumab or rituximab and polatuzumab vedotin at full dose and consider resuming lenalidomide at a reduced dosea per guidelines in Section 5.1.7.2 or continue current dose for current and subsequent cycles.
 

CT=computed tomography; DBLCL=diffuse large B-cell lymphoma; FL=follicular lymphoma; G-CSF=granulocyte colony-stimulating factor; IRR=infusion-related reaction; LMWH=low-molecular-weight heparin; NCI CTCAE=National Cancer Institute Common Terminology Criteria for Adverse Events; NSAID=nonsteroidal anti-inflammatory drug; PML=progressive multifocal leukoencephalopathy; SJS = Stevens-Johnson syndrome; TEN = toxic epidermal necrolysis; TLS=tumor lysis syndrome; ULN=upper limit of normal.

a Dose modifications apply only to events that are considered to be related to lenalidomide.

b According to Cairo-Bishop classification system.

c Graded according to NCI CTCAE, Version 3.0.

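### Section 4.1.2 and the Synopsis waive the creatinine-clearance exclusion for lymphoma-related impairment, with no floor and no renal starting dose; Section 5.1.4.8 bars the same patients without exception

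*Combined protocol and SAP*

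**What the plan says.** **Eligibility text.** In Section 4.1.2 the relevant bullet opens "Any of the following abnormal laboratory values (unless due to underlying lymphoma", and calculated creatinine clearance below 50 mL/min (Cockcroft-Gault) is the first item beneath it. The Synopsis repeats the same structure. Neither gives a lower limit.

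**Risk text.** Section 5.1.4.8 notes that lenalidomide is largely excreted by the kidney, defines renal impairment by the same 50 mL/min threshold, and says these patients "will not be enrolled in this study. Renal function will be monitored during the study, and the lenalidomide dose may be adjusted as outlined". For the adjustment it points to Section 5.1.7.2 and Table 19. It mentions no lymphoma exception and does not refer back to Section 4.1.2.

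**Dosing text.** For renal toxicity during induction, Table 19 says that at 30 to <50 mL/min "lenalidomide should be given at a dose of 10 mg/day". Below 30 mL/min it gives 10 mg every other day without dialysis and 5 mg/day with dialysis. That row carries footnote a: "Dose modifications apply only to events that are considered to be related to lenalidomide". Section 5.1.7 similarly says that "dose modifications apply only to toxicities that are considered to be related to lenalidomide or polatuzumab vedotin", the latter only for peripheral neuropathy.

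**Safeguard.** Under Section 4.2, "the study site will submit documentation supporting eligibility to the Sponsor and obtain" its approval before the patient is enrolled.

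**The concern.** The two statements give opposite answers for the same patient. Take an illustrative clearance of 35 mL/min that the investigator attributes to lymphoma: Section 4.1.2 does not exclude this patient and Section 5.1.4.8 does. The reason given in Section 5.1.4.8, renal elimination of the drug, does not depend on why clearance is low, so a waiver based on cause does not answer it.

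What is at stake is patient safety in a dose-escalation study of a renally cleared drug. The permissive text has no floor and no matching starting dose, so a waived patient's first dose would be whatever the cohort or the RP2D dictates.

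**Working it through.** No figure in the plan needs reproducing. The check compares the texts and then works out dose ratios.

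**1. Which text operates?** Section 4.1 opens by saying that the study enrols patients who meet the criteria listed there. Section 4.5.1 requires the investigator to confirm all eligibility criteria before enrolment. Section 5.1.4.8 sits in the safety narrative. The documents therefore point to Section 4.1.2, which is the permissive version.

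**2. Is there a floor or starting dose elsewhere?** The only other renal threshold found is the <70 mL/min example in Table 13, which concerns tumor lysis premedication. Section 5.1.7.2 sets out reduction steps and hold rules for lenalidomide-related toxicity. Table 19 has clearance bands, but as guidance for toxicity during induction, and footnote a ties modifications to lenalidomide-related events. Impairment caused by lymphoma before the first dose is not such an event, so whether the row applies is unclear.

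**3. How do other lymphoma-related abnormalities compare?** Table 17, footnote b, gives a dosing rule for cytopenia thought to come mainly from marrow infiltration. Table 19 gives a separate transaminase and bilirubin threshold for patients with liver involvement. There is no counterpart for lymphoma-related renal impairment.

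**4. Dose ratios.** Assigned induction doses are 10, 15 or 20 mg daily (Table 3 for FL, Table 8 for DLBCL), and the RP2D in expansion (Section 4.3.2.4). Ratio = assigned daily dose / Table 19 average daily dose. Ten mg every other day averages 10/2 = 5 mg/day.

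| Clearance (mL/min) | Table 19 average | 10 mg assigned | 15 mg assigned | 20 mg assigned |
|---|---|---|---|---|
| 30 to <50 | 10 mg/day | 10/10 = 1.0 | 15/10 = 1.5 | 20/10 = 2.0 |
| <30, no dialysis | 5 mg/day | 10/5 = 2.0 | 15/5 = 3.0 | 20/5 = 4.0 |
| <30, dialysis | 5 mg/day | 10/5 = 2.0 | 15/5 = 3.0 | 20/5 = 4.0 |

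In expansion the first row is exceeded whenever the RP2D is above 10 mg.

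**5. Duration.** The planned post-induction dose is 10 mg in both histologies (Tables 2, 5, 7 and 10). At 30 to <50 mL/min the ratio is then 10/10 = 1.0, so any excess is confined to the six induction cycles. Below 30 mL/min it would be 10/5 = 2.0 if the Table 19 bands were carried forward, which that table's title does not provide for.

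**The case against.** **Section 5.1.4.8 may be shorthand.** The protocol does paraphrase criteria without their waivers. Section 5.1.3.1 says "Patients with inadequate hematologic function will be excluded from this study", although Section 4.1.2 waives that criterion too when lymphoma is the cause. The safety plan in Section 5.1 also points to Section 4.1, saying "Eligibility criteria have been designed to exclude patients at higher risk for toxicities". This reading is plausible and is why confidence is moderate. But the hematologic sentence cites Section 4.1.2, where the exception can be found, whereas Section 5.1.4.8 gives its own number and reason with no citation. If it is only shorthand, the waiver governs and the missing floor and starting dose remain.

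**Table 19 may already protect the patient.** Its renal row is keyed to clearance, not cause, and Section 5.1.4.8 links dose adjustment to monitored renal function. A cautious investigator may well apply it from the start. That stands as mitigation, but footnote a is marked on the row and leaves its use at baseline open to dispute.

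**The Sponsor approves each patient.** This lowers the risk. It does not settle the rule, because the approval works from the same text.

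Four stronger readings are tempting and are not supported:

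- *No text indicates which statement governs.* The opening of Section 4.1 and Section 4.5.1 make Section 4.1 operative.
- *A fixed share of the cohorts assigns too much lenalidomide.* FL Cohorts 5 and 6 look like alternatives, but Section 3.1.2.1.3 allows de-escalation after the MTD is exceeded. Lowering polatuzumab vedotin from Cohort 6 yields the Cohort 5 combination. Section 6.1 only anticipates five FL cohorts, and a cohort count leaves out the expansion phase.
- *Patients assigned 10 mg are safe from any gap.* This fails below 30 mL/min.
- *The RP2D would be distorted.* One extra DLT can matter in a 3+3 cohort, but the documents give no frequency of waived patients and no effect on DLT risk.

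**Conclusion.** The eligibility rule is wrong as written: it contradicts itself in current body text, and the operative version is the permissive one. For a waived patient the possible excess in assigned induction dose over Table 19 is 1.5 or 2 times at 30 to <50 mL/min (at 15 or 20 mg). Below 30 mL/min it is at least 2 times. These are dose ratios, not estimates of exposure or toxicity.

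The conclusion assumes that sites follow Section 4.1.2 literally, that low clearance is attributed to lymphoma, that the Sponsor approves the enrolment, and that Table 19 is not applied at baseline. Each step is possible under the text and none is certain. The number of affected patients is unknown and probably small. Sample size, endpoints and the primary analysis are unaffected. The change should be made; confidence is moderate.

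**What to change.** In Section 4.1.2 and the Synopsis, take calculated creatinine clearance below 50 mL/min (Cockcroft-Gault) out of the list governed by the lymphoma waiver and make it a stand-alone exclusion, matching Section 5.1.4.8. In Section 4.1.2 keep the reference to Appendix 7. The transaminase, bilirubin and coagulation items keep the waiver.

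The cost is one bullet moved in two places at the next amendment. The downside is that patients with lymphoma-related renal impairment cannot enter, which Section 5.1.4.8 already says.

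If the Sponsor prefers to keep the waiver for creatinine clearance, it would need a stated floor, a renal starting dose, and a revised Section 5.1.4.8. That is a larger change.

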## 4.2 METHOD OF TREATMENT ASSIGNMENT

This is a Phase Ib/II, open-label, multicenter, non-randomized, dose-escalation study of G+Pola+Len in patients with R/R FL and R+Pola+Len in patients with R/R DLBCL.

During the dose-escalation phase, patients will be assigned to cohorts with varying polatuzumab vedotin (*R/R FL dose-finding only*) and lenalidomide dose combinations, through use of an interactive voice or web-based response system (IxRS). During the *FL* expansion phase, patients *with R/R FL* will receive obinutuzumab in combination with lenalidomide at the *FL* RP2D and polatuzumab vedotin at the RP2D as induction treatment. *During the DLBCL expansion phase, patients with R/R DLBCL will receive rituximab and polatuzumab in combination with lenalidomide at the DLBCL RP2D.* Post-induction treatment (for eligible patients only) will depend on lymphoma histology. Patients with *FL* will receive maintenance treatment with obinutuzumab and lenalidomide, and patients with *DLBCL* will receive consolidation treatment with *rituximab* and lenalidomide (see Section 3.1.1 for details).

Enrollment tracking will be performed through use of the IxRS. Prior to initiating screening, the study site should confirm via the IxRS that slots are available for enrollment. After written informed consent has been obtained and preliminary eligibility has been established, the study site will submit documentation supporting eligibility to the Sponsor and obtain the Sponsor's approval to enroll the patient. Once the Sponsor reviews and approves the patient for enrollment, the patient number will be assigned and the patient will be enrolled via the IxRS. The Sponsor will communicate to the sites impending closure of screening.

